	16.2.1 Sample listing	
	. 5	

LIST OF ABBREVIATIONS

ADE	Adverse Device Effect
AE	Adverse Event
CIP	Clinical Investigation Plan
CRF	Case Report Form
CRO	Contract Research Organization
CTCAE	Common Terminology Criteria for Adverse Events
DLQI	Dermatology Life Quality Index questionnaire
FAS	Full Analysis Set
GCP	Good Clinical Practice
GMP	Good Manufacturing Practice
ICH	International Conference on Harmonization
IFU	Instructions For Use
IGA	Investigator Global Assessment
IEC	Indipendent Ethics Committee
MedDRA	Medical Dictionary for Regulatory Activities
PPAS	Per-Protocol Analysis Set
РТ	Preferred Term
ml	Milliliters
SADE	Serious Adverse Device Effect
SAF	Safety Analysis Set
SAE	Serious Adverse Event
SGA	Scar Global Assessment
SOC	System Organ Class
SOP	Standard Operating Procedure
USADE	Unanticipated Serious Adverse Device Effect

1. VERSION HISTORY

1.1 Version history of the SAP

Version Number	Summary/Reason for changes	Date issued
1.0	First version	30/07/2021
2.0	SAP amendment to correct the efficacy endpoints	09/11/2021

1.2 Version history of the Protocol

Version Number	Date	Description
1.0	02/12/2019	First version submitted
2.0	02/07/2020	The protocol was amended in order to correct the number of tubes of the investigational product dispensed to the study subject.

1.3 Version history of the CRF

Version Number	Date	Description
1.0	13/02/2020	First version in production

2. INTRODUCTION

The clinical investigation ReGl/19/PAS-Acn/001 was conducted to evaluate the clinical performance and safety of PAPIX ACNE SCAR in the treatment of acne scars and lesions.

Acne vulgaris is a common and widespread dermatological disorder that predominantly affects teenagers but can also affect preadolescents and post-teen individuals. In general, the prevalence of scars increases with acne severity, in the presence of large lesions and severe inflammation, but also subjects with mild acne are at risk of scarring. There are no general guidelines available to optimize acne scar treatment. However, there is a variety of therapies that may reduce the prominence of acne scars.

PAPIX ACNE SCAR, the medical device tested in the present post market clinical follow-up investigation, is a silicone gel indicated for acne lesions and scars; this acts by creating a sheer physical barrier that separates the skin from surrounding environment, useful for generating favorable conditions for the maintenance and/or recovery of the physiological cutaneous layer in case of acne lesion. Thus, PAPIX ACNE SCAR improves skin by keeping it hydrated and works to prevent and reduce acne scars, also thanks to the presence of humectant/moisturizing ingredients.

The present study was conducted in Italy with the purpose of confirming and supporting the CE mark of PAPIX ACNE SCAR in the post-market phase. In this post-market clinical follow-up investigation PAPIX ACNE SCAR

was used according to its Instructions for Use (IFU), in males and females ≥ 12 years of age, affected by mild to moderate acne.

3. STUDY OBJECTIVES

3.1 Primary Objectives

The primary objective of this clinical investigation was to evaluate and confirm the performance of PAPIX ACNE SCAR in the prevention and improvement of acne scars in subject suffering for mild to moderate acne, after 4 weeks of treatment.

3.2 Secondary Objectives

The secondary objectives of this clinical investigation were:

- 1. To evaluate the performance of PAPIX ACNE SCAR in the prevention and improvement of acne scars after 2 and 8 weeks of treatment.
- 2. To evaluate the performance of PAPIX ACNE SCAR in the prevention of acne lesions after 2, 4 and 8 weeks of treatment.
- 3. To evaluate the improvement in acne severity after 2, 4 and 8 weeks of treatment, through the Investigator Global Assessment, ranging from 0 (clear; clear skin with no lesions) to 4 (severe; many inflammatory and non- inflammatory lesions).
- 4. To evaluate the improvement of the skin roughness on a 4-point scale from 0 (none; very smooth) to 3 (severe; very rough) after 2, 4 and 8 weeks of treatment.
- 5. To evaluate the improvement of the skin texture on a 6-point scale from 0 (worse) to 5 (complete improvement), after 2, 4 and 8 weeks of treatment.
- 6. To evaluate the subject's and Investigator's global evaluation of satisfaction with regards to the performance of PAPIX ACNE SCAR, through a specific questionnaire.
- 7. To evaluate the subject's overall acceptability of PAPIX ACNE SCAR, through a specific questionnaire.
- 8. To evaluate the subject's adherence to treatment by the product accountability and information asked to the subject.

4. STUDY METHODS

4.1 Study Design

This was a multicenter, open label, uncontrolled, post-market clinical follow-up investigation.

All the subjects were allocated to the following treatment group:

- PAPIX ACNE SCAR, topically applied twice a day for 8 weeks.

The subject started treatment on the first day of study and continued for 8 weeks after the first administration.

4.2 Treatment Administration

Subjects were instructed to use PAPIX ACNE SCAR applied twice a day, in the morning and in the evening before bedtime, and massaged gently into the skin until absorbed. The treatment duration was of 8 weeks.

4.3 Randomization and Blinding

Not applicable: open-label clinical investigation.

5. STUDY ENDPOINTS

5.1 Primary Endpoints

Proportion of subjects with improved acne scars and marks at week 4 of treatment (Visit 3) and, at the same time, without any new facial acne scars with respect to baseline (Visit 1).

5.2 Secondary Endpoints

Secondary endpoints were:

- 1. Proportion of subjects with improved acne scars and marks at week 2 and 8 of treatment (Visits 2 and 4) and, at the same time, without any new facial acne scars with respect to baseline (Visit 1).
- 2. Proportion of subjects at week 2, 4 and 8 of treatment, without any new facial acne lesions with respect to baseline (Visit 1).
- 3. Change from baseline (Visit 1) to each following time point in the acne severity, according to the Investigator Global Assessment.
- 4. Change from baseline (Visit 1) to each following time point in the skin roughness, on a 4-point scale from 0 (none; very smooth) to 3 (severe; very rough).
- 5. Change from baseline (Visit 1) to each following time point in the skin texture on a 6-point scale from 0 (worse) to 5 (complete improvement).
- 6. The subject's adherence to treatment by the product accountability.
- 7. The subject's and Investigator's global evaluation of satisfaction with regards to the performance of PAPIX ACNE SCAR, through a specific questionnaire.
- 8. To evaluate the subject's overall acceptability of the treatment, through a specific questionnaire.

5.3 Safety Endpoints

To evaluate the local and general tolerability of PAPIX ACNE SCAR. Adverse events and adverse reactions were recorded and evaluated.

6. PLANNED ANALYSIS

6.1 Interim Analysis

No interim analysis is planned.

6.2 Final Analysis

Final analysis will be performed according to the protocol and to this Statistical Analysis Plan, after data cleaning operations and DB Lock will be performed. The statistical analysis will be performed using SAS 9.4 for Windows (SAS Institute Inc., Cary, NC, USA).

7. SAMPLE SIZE AND STATISTICAL POWER CONSIDERATION

An exact binomial test with a nominal 5% two-sided significance level has 80% power to detect the difference between the Null hypothesis proportion, π_0 of 0.5 (i.e., 50% of subjects with treatment success) and the Alternative

proportion, π_1 , of 0.75 (i.e., 75% of subjects with treatment success) when the sample size is 30 subjects. Assuming a possible 25% dropout rate, 40 subjects were enrolled, according to the CIP provisions.

8. ANALYSIS POPULATIONS

8.1 Full Analysis Set (FAS)

The FAS population includes all subjects of the safety population who have performed the baseline assessments and had at least one post-baseline assessment of any performance endpoint (primary or secondary).

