6.4 Procedures

6.4.1 Study Visits and Assessments

Visit 1 screening – baseline- treatment start (day 1):

Subjects will be evaluated with regard to the inclusion and exclusion criteria that will allow their participation into the study.

Before any study specific evaluation is carried out, subjects will receive all the information about the study by the Investigators and will sign an informed consent form. In the case of minors, the informed consent form shall be signed by the parents or the guardian.

The following activities will be performed:

- Collection of information about demography
- Medical and surgical history
- Acne medical history (duration, previous treatments)
- Physical examination (only dermatologic)
- Face cutaneous examination:
 - type of skin (dry/normal/oily)
 - site of acne lesions (on the face) and count
 - acne scars count
 - acne scars global assessment by the SGA
 - acne global assessment by IGA
 - roughness and skin texture evaluations
- Photographs of the face
- Previous (in the 6 months before) and concomitant medications/treatments recording
- Inclusion/exclusion criteria assessment
- Study product delivery to subject and instructions on how to use it
- Recommendations for face cleaning to follow.

Recommendations for face cleaning to follow: throughout the study subjects will be required to avoid soap and use only the product Papix cleanser for their face. The product will be provided by the Sponsor of the study. No other cleanser other than the product provided by the Investigator will be permitted.

PAPIX ACNE SCAR application: apply twice a day for 8 weeks, 2 FTU (finger tip units) in the morning and in 2 FTU the evening before bedtime, on the face, and massaged gently into the skin until absorbed.

Visits 2 and 3 – follow-up (Day 14 ± 3 and 28 ± 3, respectively):

The following activities will be done at visit 2 and 3:

- Face cutaneous examination:
 - acne scars and lesions count
 - acne scars global assessment by the SGA
 - acne global assessment by IGA
 - roughness and skin texture evaluations
- Photographs of the face
- Changes in concomitant medications/treatments recording
- Study product collection and new delivery to subject (only at visit 3)
- Treatment adherence check with the subject
- Recommendations for face cleaning to follow
- Adverse events (occurred since previous visit) recording.

Visit 4 – End of treatment and end of study (Day 56 ±3):

The following activities will be done at visit 4:

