7.2 Definition of Study Populations for Analysis

The following populations are defined for this investigation:

- Safety analysis set (SAF): all patients enrolled who sign informed consent and receive at least one administration of the investigational device.
- Full analysis set (FAS): all patients of the SAF who have performed the baseline assessments and have at least one post-baseline assessment of any performance endpoint (primary or secondary).
- Per-Protocol analysis set (PPAS): all patients of the FAS who also meet all inclusion/exclusion criteria and who do not have any major protocol deviation (i.e. wrong inclusion, use of forbidden concomitant medications, etc.).

The analysis of safety endpoints will be performed in the Safety population (SAF). Analysis of performance endpoints will be performed on the FAS population. The analysis of primary endpoint will be repeated in the PPAS.

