8.2 Per-Protocol (PP) Population

The PP population includes all subjects of the FAS who also met all inclusion/exclusion criteria and who did not have any major protocol deviation (i.e. wrong inclusion, use of forbidden concomitant medications, etc.).

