8.3 Safety Population

The Safety Population includes all the subjects enrolled who signed informed consent and received at least one administration of the investigational device.

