9.1.4 Methods for Withdrawals and Missing Data

Missing data will not be replaced in any statistical analysis.

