11. EFFICACY ANALYSIS

11.1 Analysis datasets

The analysis of safety endpoints will be performed in the Safety population (SAF). Analysis of performance endpoints will be performed on the FAS population. The analysis of primary endpoint will be repeated in the Per-Protocol population.

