11.4 Efficacy Analysis

11.4.1 Primary Efficacy Endpoints

The primary endpoint will be the proportion of subjects with acne scars and marks improved with respect to baseline and, at the same time, without any new facial acne scars after 4 weeks of treatment (treatment success). The improvement of acne scars and marks will be assessed as the change of at least one grade in the qualitative Scar Global Assessment (SGA) by Goodman and Baron between baseline and Week 4. The number of new acne scars will be assessed by count and comparison with baseline.

The primary endpoint will be described using number (N) and the proportion of subjects (%) in the Tables 14.2.1.1 and 14.2.1.2. The proportion of treatment successes will be compared to a referent proportion (50%, Null hypothesis proportion) using the exact binomial test.

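### Treated subjects with no post-baseline assessment are in no performance denominator, which may inflate the single-arm Week 4 success rate; a line over all treated subjects would guard against this

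*SAP*

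**What the plan says.** Three rules act together.

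- **Who is analysed.** The Safety set is everyone who consented and "received at least one administration of the investigational device" (SAP 8.3). The FAS is narrower: Safety-set subjects with baseline assessments who also "had at least one post-baseline assessment of any performance endpoint (primary or secondary") (SAP 8.1). Protocol 7.2 has the same condition: "have at least one post-baseline assessment of any performance endpoint (primary or secondary").
- **Where the sets are used.** "Analysis of performance endpoints will be performed on the FAS population" (SAP 11.1). The primary endpoint is repeated in the PP set, but "The PP population includes all subjects of the FAS" who meet further conditions (SAP 8.2). Every efficacy table in SAP 14.2 is FAS or PP.
- **Missing data.** "Missing data will not be replaced in any statistical analysis" (SAP 9.1.4; Protocol 7.3.1 says the same).

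The first scheduled post-baseline assessments are Visits 2 and 3, described as "follow-up (Day 14 ± 3 and 28 ± 3, respectively") in Protocol 6.4.1. The primary result is one proportion, "compared to a referent proportion (50%, Null hypothesis proportion) using the exact binomial test" (SAP 11.4.1). Neither document says whether the Week 4 denominator is the whole FAS or only those observed at Week 4.

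The flow chart lets Visit 4 serve as an early-termination visit, and Protocol 16.1 asks for its pages to be completed for discontinued subjects where this can be done. SAP 10.1 plans disposition by visit with reasons for withdrawal (Table 14.1.1). SAP 16.2 plans listings of discontinued subjects (16.2.1) and of subjects excluded from the efficacy analysis (16.2.3).

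**The concern.** FAS membership depends on something that happens after treatment starts: remaining long enough to be assessed once. A treated subject who leaves before Visit 2 with no early-termination assessment counts for safety and for nothing else. The PP set cannot bring that subject back.

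In a controlled trial, similar early losses in both arms may partly cancel. Here the comparator is a fixed number, so nothing offsets a selective loss. Some discontinuation reasons in Protocol 16.1 (adverse events, poor compliance, need for a treatment that is not allowed) plausibly go with a lower chance of success. If so, removing these subjects raises the observed proportion. With 30 to 40 subjects, a few exclusions can decide whether the test against 50% is significant.

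**Working it through.** **Inputs from the documents.** Two-sided 5% exact binomial test; null 0.50; alternative 0.75; 30 evaluable; 25% dropout; 40 enrolled (Protocol 7.1, SAP 7).

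**Assumptions.** All 40 enrolled subjects are treated. The number k lost with no post-baseline assessment is not given, so a range is shown. The 25% allowance, 10 of 40, covers dropout at any time and is therefore an extreme upper limit for k.

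**1. The plan's own figures.** At n = 30 the smallest significant count is 21: P(X ≥ 21 | 0.5) = 0.0214, two-sided 0.043. Power is P(X ≥ 21 | 0.75) = 0.803. Enrolment is 30/(1 − 0.25) = 40. Both stated figures reproduce, and the sample size is not in question.

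**2. Size of the shift.** Excess of the analysed rate over the all-treated rate = (share lost) × (success in retained − success in lost). With 75% success in those retained:

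| Success in those lost | 1 of 40 lost | 4 of 40 lost |
|---|---|---|
| 0% | +1.9 points | +7.5 points |
| 50% | +0.6 | +2.5 |
| 75% | 0 | 0 |
| 100% | −0.6 | −2.5 |

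The worst case per subject is (1/40) × 75 = 1.875 points.

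**3. Effect on the test.** Suppose the rate over all 40 is 50% and every lost subject is a non-success. Those retained then succeed with probability 20/(40 − k). The chance of a favourable significant result is P(X ≥ r | 40 − k, 20/(40 − k)), where r is the smallest significant count:

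| k lost | n | r | Retained rate | Chance |
|---|---|---|---|---|
| 0 | 40 | 27 | 0.500 | 1.9% |
| 1 | 39 | 27 | 0.513 | 1.8% |
| 2 | 38 | 26 | 0.526 | 3.6% |
| 4 | 36 | 25 | 0.556 | 6.4% |
| 5 | 35 | 24 | 0.571 | 11.5% |

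The nominal upper tail is 2.5%. The rise is not smooth because the test is discrete. If success is 50% in lost and retained subjects alike, the same tail is 1.7%, 1.4% and 2.0% for k = 2, 4 and 5, so there is no inflation.

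**4. Boundary examples.** 26/38 = 68.4%, p = 0.034, against 26/40 = 65.0%, p = 0.081. 24/35 = 68.6%, p = 0.041, against 24/40 = 60.0%, p = 0.268. Both use the minimum passing count at that n; 23/35 already fails, with p = 0.090. They show that a reversal is possible, not that it is likely.

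**5. Which rule does the work.** Suppose the FAS were widened to all treated subjects but missing data were still not replaced, and the Week 4 rate used observed cases. A subject lost before Visit 2 would still be absent from that rate. A subject seen at Visit 2 and lost before Visit 3 is in the FAS already, yet may drop out of the Week 4 denominator in the same way. The FAS condition and the missing-data rule therefore have to be handled together.

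**The case against.** A reader might infer that the FAS definition is known to bias the result upward. The documents do not establish this. Protocol 16.1 also lists loss to follow-up and withdrawal of consent, which need not be related to response, and step 2 shows that the shift is zero or negative if those lost would have done as well or better. A single lost subject does not raise the false-positive chance even when counted as a failure.

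A reader might also apply the whole 25% allowance to this group and conclude that the rate could be inflated by 25% × 75 = 18.8 points. Nothing supports that: the allowance has no timing and covers all dropout.

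The excluded group may be small or empty. One assessment of any performance endpoint is enough to enter the FAS, and an early-termination assessment counts. The planned disposition table and listings will show who was left out. It is also fair to say that the FAS condition alone does not drive the Week 4 rate, since the no-replacement rule would remove the same subjects from an observed-case analysis.

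All of this limits the size and certainty of the point. What stands is that no planned performance analysis includes these subjects, and that showing exclusions in a listing does not correct the estimate or the p-value.

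**Conclusion.** The gap is real, conditional in direction and unknown in size. Under SAP 8.1 and 9.1.4 with Protocol 7.2 and 7.3.1, a treated subject with no post-baseline assessment is in no performance denominator. This may bias the Week 4 success rate upward if subjects lost early succeed less often than those retained. That is plausible but remains an assumption.

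The bound is about 1.9 points per subject lost, given 75% success in those retained and none in those lost. With an all-treated rate of 50% and all lost subjects non-successes, the false-positive chance exceeds the nominal 2.5% at two lost (3.6%) and reaches 11.5% at five. The stronger reading, that the FAS clause by itself causes a definite upward bias, is not supported: direction depends on outcomes that are not observed, and the missing-data rule shares the mechanism. The point is worth acting on because the primary claim rests on one small uncontrolled proportion and the safeguard is cheap.

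**What to change.** Add a line to Table 14.2.1.1, labelled with its own denominator, giving Week 4 successes over all Safety-set subjects who have a Visit 1 SGA and scar count, with its exact binomial test against 50%. Count every subject without a Week 4 outcome as not successful, whether lost before Visit 2 or between Visits 2 and 3, so that one rule covers both. State this as an explicit exception to SAP 9.1.4 and Protocol 7.3.1. If the protocol is not amended, record the exception in SAP section 13, which at present declares no deviations.

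Alternatively, delete the post-baseline condition from SAP 8.1 and Protocol 7.2 and apply the same rule in the primary analysis. Deleting the condition without the rule would not be enough.

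Numbers and reasons for exclusion need no new output: cross-refer to Table 14.1.1 and Listings 16.2.1 and 16.2.3.

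The cost is some SAP wording and one table line (for the alternative, protocol wording as well), with no new data. The reported rate may be lower, and it is conservative if some lost subjects would have succeeded. If every such subject has a Week 4 outcome, the new line equals the FAS result and shows that it does not depend on exclusions.

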8.2 Per-Protocol (PP) Population

The PP population includes all subjects of the FAS who also met all inclusion/exclusion criteria and who did not have any major protocol deviation (i.e. wrong inclusion, use of forbidden concomitant medications, etc.).

8.3 Safety Population

The Safety Population includes all the subjects enrolled who signed informed consent and received at least one administration of the investigational device.

9. GENERAL ISSUES FOR STATISTICAL ANALYSIS

9.1 Definitions, Derived Variables and Datasets

Variable	Туре	Description
lesion_num	Continous	Number of lesions
scar_num	Continous	Number of scars
srorres_iga	Discrete	Investigator's Global Assessment: 0 = Clear skin 1 = Almost clear skin 2 = Mild severity 3 = Moderate severity 4 = Severe
srorres_sga	Discrete	Scar Global Assessment: 0 = Clear skin 1 = Almost clear skin 2 = Mild severity 3 = Moderate severity 4 = Severe
srorres_rough	Discrete	Skin roughness assessment:0 = None, very smooth1 = Mild, slightly rough2 = Moderate, rough3 = Severe, very rough
srorres_texture	Discrete	Skin texture assessment: 0 = worse 1 = slightly worse 2 = no change 3 = slightly improved 4 = improved

		5 = complete improvement
qsorres_perf_subj	Discrete	Subject's global evaluation of performance: 1 = Very much improved 2 = Improved 3 = Minimally improved 4 = No change 5 = Minimally worse 6 = Worse
qsorres_perf_inv	Discrete	7 = Very much worseInvestigator's global evaluation of performance:1 = Very much improved2 = Improved3 = Minimally improved4 = No change5 = Minimally worse6 = Worse7 = Very much worse
qsorres_satisf	Discrete	Subject's overall acceptability: 1 = Very much satisfied 2 = Satisfied 3 = Neither satisfied nor dissatisfied 4 = Dissatisfied 5 = Very much dissatisfied
ecoccur	Discrete	Compliance
ecdur	Continous	Treatment skipped times
aeterm	Discrete	Adverse event description

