6.3.1 Inclusion criteria

1. Subject's or parents or guardian (depending on the age of the subject) written informed consent obtained prior to any study-related procedures;
2. Male or female subjects aged ≥ 12 years of any race;
3. Subjects with any Fitzpatrick skin phototype;
4. Subjects with clinical diagnosis of mild to moderate acne vulgaris (IGA score 2 or 3) on the face
5. Presence of acne scars (all types included), of grade mild or moderate according to SGA;

6. Subjects with cooperative attitude, able to comprehend the full nature and the purpose of the investigation, including possible risks and side effects, and able to comply with the requirements of the entire investigation (including ability to attend the planned visits according to the time limits), based on Investigator's judgement.

6.3.2 *Exclusion criteria*

1. Pregnant women
2. Severe acne at inclusion or any acne requiring systemic treatment;
3. Presence of facial warts or fungal infections;
4. Active dermatitis on the face, rosacea, active herpes simplex;
5. Keloids presence in the area to be treated or keloids development during the treatment period;
6. History of radiation or skin tumors in the/close to the area to be treated in the past 5 years;
7. Laser ablative procedures within the last month;
8. Chemical peels within the last 6 months;
9. Use of topical treatments like antibiotics, corticosteroids, benzoyl peroxide, azelaic acid, hydroxy acids and other anti-inflammatory drugs within 2 weeks;
10. Use of topical retinoids within 4 weeks;
11. Use of systemic corticosteroids or antibiotics in the previous 30 days;
12. Use of systemic spironolactone/drospirenone or immunomodulators in the previous 3 months;
13. Use of oral retinoids or cyproterone acetate/chlormadinone acetate in the previous 6 months;
14. Use of scrub, alpha hydroxy acid (AHA), skin irritant products in the 2 days before study treatment start;
15. Subjects with any other clinically significant or unstable concurrent disease or skin condition or general condition that, in the Investigator's opinion, might interfere with the study evaluations;
16. Allergy, sensitivity or intolerance to the components of the investigational device formulations ingredients;
17. Concomitant or previous participation in other interventional clinical study in the past 3 months;

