6.4.2 Scar Global Assessment (SGA)

The qualitative scarring grading system proposed by Goodman and Baron [26] is simple and universally applicable. According to this classification, four different grades can be used to identify an acne scar, as shown in the table below.

Qualitative scarring grading system SGA.

Grades of Post Acne Scarring	Level of disease	Clinical features
1	Macular	These scars can be erythematous, hyper- or hypopigmented flat marks. They do not represent a problem of contour like other scar grades but of color.
2	Mild	Mild atrophy or hypertrophy scars that may not be obvious at social distances of 50 cm or greater and may be covered adequately by makeup or the normal shadow of shaved beard hair in men or normal body hair if extrafacial.
3	Moderate	Moderate atrophic or hypertrophic scarring that is obvious at social distances of 50 cm or greater and is not covered easily by makeup or the normal shadow of shaved beard hair in men or body hair if extrafacial, but is still able to be flattened by manual stretching of the skin (if atrophic).
4	Severe	Severe atrophic or hypertrophic scarring that is evident at social distances greater than 50 cm and is not covered easily by makeup or the normal shadow of shaved beard hair in men or body hair if extrafacial and is not able to be flattened by manual stretching of the skin.

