6.4.3 Acne Investigator's Global Assessment (IGA)

IGA is a tool used in the clinical routine to define acne vulgaris severity. The Investigator's Global Assessment is based on a 5-point scale:

Investigator's Global Assessment (IGA) for acne vulgaris

Grade	Description
0	Clear skin with no inflammatory or non-inflammatory lesions
1	Almost clear; rare non-inflammatory with no more than one small inflammatory lesion
2	Mild severity; greater than Grade 1; some non-inflammatory lesions with no more than a few inflammatory lesions (papules/pustules only; no active nodulo-cystic lesions)
3	Moderate severity; greater than Grade 2; up to many non-inflammatory lesions and may have some inflammatory lesions, but no more than one active small nodular lesion
4	Severe; greater than Grade 3; up to many non-inflammatory and inflammatory lesions, but no more than a few active nodular lesions

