7.3.5 Efficacy analysis

7.3.5.1 Primary endpoint

The primary objective of this clinical investigation is to evaluate and confirm the performance of PAPIX ACNE SCAR in the prevention and improvement of acne scars, in terms of improvement of visible acne scars and marks from baseline and prevention of new acne scars, in subject suffering for mild to moderate acne, after 4 weeks of treatment.

The primary endpoint will be the proportion of subjects with acne scars and marks improved with respect to baseline and, at the same time, without any new facial acne scars after 4 weeks of treatment (treatment success). The improvement of acne scars and marks will be assessed as the change of at least one grade in the qualitative Scar Global Assessment (SGA) by Goodman and Baron [26] between baseline and Week 4. The number of new lesions will be assessed by count and comparison with baseline.

The primary endpoint will be described using number (N) and the proportion of patients (%). The proportion of treatment successes will be compared to a referent proportion (50%, Null hypothesis proportion) using the exact binomial test.

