Changes to the clinical investigation plan may only be made by means of a written amendment, which has to be approved and signed by the authorized representatives of the Sponsor, and by the Investigator.

Exhaustive justifications that motivate the amendment to the clinical investigation plan should clearly be addressed in the document.

All substantial Clinical Investigation Plan amendments must be submitted for approval to IEC and notified to the Regulatory Authority. In case of non-substantial amendment the IEC and the Regulatory Authority (when applicable) will be only notified of the amendment without the request to review and approve it.

The Investigator, the Sponsor and IEC, separately or together, should decide whether the subject's informed consent form needs to be changed.

10. Deviations from Clinical Investigation Plan

The Investigator is to conduct the study in accordance with the relevant, current clinical investigation plan and will only deviate when necessary to protect the safety, rights and welfare of the subjects. In the event that an isolated, unforeseen instance occurs resulting in a clinical investigation plan deviation, the Investigator is to document this deviation and notify the CRO or the Sponsor as soon as possible. In no instance should this increase the subject's risk or affect the validity of the study.

11. Device Accountability

The Investigator is responsible of ensuring accountability of the study product, including reconciliation of study product and maintenance of records.

Upon receipt of the study product, the Investigator (or designee) will check the contents and acknowledge receipt by signing (or initialing) and dating the documentation provided by the Sponsor and returning it to the Sponsor. A copy will be retained in the Investigator File.

The dispensing of the study product will be carefully recorded on the appropriate accountability forms provided by the Sponsor and an accurate accounting will be available for verification by the Study Monitor at each monitoring visit.

Study product accountability records will include:

- Confirmation of study product receipt at the clinical site.
- The inventory at the site of study product provided by the Sponsor.
- The tubes delivery to each subject.
- The tubes return from each subject.
- The return to the Sponsor or alternative disposition of unused study product.

The Investigator should maintain records that adequately document:

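### SAP 9.1 codes the Scar Global Assessment with the acne IGA labels (0 to 4) instead of the protocol's four scar grades (1 to 4)

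*SAP*

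**What the plan says.** Protocol 6.4.2 introduces the SGA as a published qualitative scar grading in which "four different grades can be used to identify an acne scar". The grades are 1 macular, 2 mild, 3 moderate and 4 severe. Grade 1 covers flat, discoloured marks, of which the protocol says "They do not represent a problem of contour like other scar grades but of color". There is no grade 0 and no clear or almost clear level.

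Those two levels belong to the acne scale in Protocol 6.4.3, where grade 1 reads "Almost clear; rare non-inflammatory with no more than one small inflammatory lesion".

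SAP 9.1 lists the analysis variables. Its row for `srorres_sga` reads "Scar Global Assessment: 0 = Clear skin 1 = Almost clear skin 2 = Mild severity 3 = Moderate severity 4 = Severe". The row above it, `srorres_iga`, carries the same five labels.

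SAP 11.4.1 sets the responder rule for Week 4: "The improvement of acne scars and marks will be assessed as the change of at least one grade" on the SGA. Protocol 7.3.5.1 has the same rule, and SAP 11.4.2 repeats it for Weeks 2 and 8. The other half of the endpoint, no new scars, uses the scar count (`scar_num`).

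Entry requires "Presence of acne scars (all types included), of grade mild or moderate according to SGA" (Protocol 6.3.1). SAP 13 states that the SAP departs from none of the protocol's analyses.

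**The concern.** The SAP refers to the SGA in two incompatible ways. Section 11.4.1 names the published scar grading, which the protocol sets out with four grades. Section 9.1 defines the variable that will hold it with a five-level list taken from a different instrument. The row survived into SAP version 2.0, which was issued to correct the efficacy endpoints.

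The conflict sits at the bottom of the scale, where success is decided for anyone entering at mild. If scoring followed the 0 to 4 labels, some subjects could be classed as improved or not improved differently from what the protocol's definition would give. The primary test and the Week 2 and Week 8 responder tests would all inherit the difference.

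**Working it through.** **1. The plan's own figure.** Inputs from SAP 7: null 0.50, alternative 0.75, two-sided 5%, n = 30, dropout 25%.

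- Critical count: 2 × P(X ≥ 21 | 30, 0.50) = 0.0428, which is at most 0.05. With 20 successes the two-sided p-value is 0.099. The test therefore needs 21 of 30.
- Power: P(X ≥ 21 | 30, 0.75) = 0.803, against the stated 80%.
- Enrolment: 30 / (1 − 0.25) = 40, as stated.

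The figures reproduce. None of the inputs depends on how SGA grades are labelled, so sample size and planned power are unaffected.

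**2. The two code lists side by side.**

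| Code | Protocol 6.4.2 | SAP 9.1 | Comparison |
|---|---|---|---|
| 0 | not defined | clear skin | no protocol counterpart |
| 1 | macular (colour, not contour) | almost clear skin | same number, different meaning |
| 2 | mild | mild | same severity word |
| 3 | moderate | moderate | same severity word |
| 4 | severe | severe | same severity word |

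**3. The responder rule under each list.** Improvement is read as baseline code minus follow-up code ≥ 1.

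| Baseline | Success levels, protocol | Success levels, SAP 9.1 |
|---|---|---|
| 2 (mild) | 1 | 0, 1 |
| 3 (moderate) | 1, 2 | 0, 1, 2 |

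Under both lists success is any code below baseline, so relabelling stored codes does not change which drops count. For a subject entering at moderate, codes 0, 1 and 2 all count, and confusion among them does not alter success. For a subject entering at mild, success turns on the boundary between 2 and the levels below it, and no success level there has a label common to both lists.

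**4. What could differ if raters used the SAP labels.** These cases show direction only, for a subject entering at mild. The documents do not show that any of them occurred.

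- Only flat coloured marks remain: protocol grade 1, a success. On the 0 to 4 labels a rater might choose 1 or 2, so success could be lost.
- Faint mild scarring remains: protocol grade 2, not a success. A rater might call it almost clear (1), so success could be gained.
- No scars remain: SAP code 0, a success. The protocol scale has no grade for this state.

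The errors can run either way. The documents give neither the baseline split between mild and moderate nor the CRF, so no count follows.

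**The case against.** The best defence is that this is a copy error in a data dictionary and the operative rule is intact. SAP 11.4.1 and 11.4.2 still name the correct scale, codes 2 to 4 match, entry is limited to mild and moderate, and any drop in code counts under either list. The SAP row is also unlikely to have driven the scoring. CRF version 1.0 is dated 13/02/2020, whereas SAP version 1.0 is dated 30/07/2021 and describes the study in the past tense. Level 0 may even be a sensible extension, since the protocol scale cannot record a face without scars.

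Most of this stands, and it limits the size of the point. It does not remove it. A SAP should define its primary variable correctly, the CRF is not among the documents, and a practical extension at 0 would still leave code 1 mislabelled.

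A reader might infer that the primary endpoint was scored on the wrong scale, or that the SAP list makes success easier. The documents support neither. They do not show what raters used, and the extra level 0 lies below a level that already counts as success.

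A reader might also note that at the planned 75% rate (22 or 23 of 30) a net loss of 2 or 3 successes would bring the count to 20 and lose significance. That is true of any binary endpoint tested at this size, and it does not estimate this error.

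**Conclusion.** The SAP's definition of `srorres_sga` is wrong as written. It conflicts with Protocol 6.4.2 at codes 0 and 1, and SAP 13 does not declare the difference. It should be fixed before lock.

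Confidence is high for the mismatch, which is visible in the text. The consequence for the result is not derivable. It is nil if CRF version 1.0 recorded the protocol's grades. If raters worked from the 0 to 4 labels, it is unknown in both size and direction and falls mainly on subjects who entered at mild. The new-scar component is not touched. The verdict assumes that improvement means a fall of at least one grade.

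**What to change.** Before database lock, for example at the Data Review Meeting in SAP 10.2, check the SGA code list in CRF version 1.0 and reconcile SAP 9.1 with Protocol 6.4.2.

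- **If the protocol grades were recorded:** correct the row to 1 macular, 2 mild, 3 moderate, 4 severe. State how a face with no remaining scars is coded, for example a labelled level 0 for no scars, counted as improved and noted as an addition to the protocol scale.
- **If the 0 to 4 labels were used for scoring:** declare this in SAP 13 and in the report. Establish whether raters nevertheless applied the Protocol 6.4.2 criteria. Fix in writing, before analysis, how codes 0 and 1 relate to the protocol grades. A stored almost clear code cannot be assigned to macular or mild from the code alone, but face photographs were scheduled at every visit and may be used to check. Describe the result as the protocol-defined SGA endpoint only if that link is confirmed. Apply the same treatment at Weeks 2 and 8.

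The cost in the first case is a code-list check, one SAP row and one sentence. The second case adds a declared deviation, a written rule and possibly a check of existing photographs. Neither needs more patients or visits.
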